## **7. GENERAL ISSUES FOR STATISTICAL ANALYSIS**

### **7.1 General Statistical Methodology**

Descriptive summaries will be provided where appropriate for each of the primary and secondary variables. In general, tables will summarize data by treatment group and visit.

Baseline characteristic and safety tables will be completed for the Safety Population unless otherwise specified. Efficacy tables will be presented for the mITT Population.

Continuous, quantitative, variable summaries will include the number of participants (N) with non-missing values, mean, standard deviation (SD), median, minimum, and maximum.

Categorical, qualitative, variable summaries will include the frequency and percentage of participants who are in the particular category. In general, the denominator for the percentage calculation will be based upon the total number of participants in the study population for the treatment group unless otherwise specified.

Baseline values are defined as the last non-missing measurement prior to the first dose of study drug. Change from baseline will be defined as the post-baseline visit value minus the baseline value.

ET participants will only be followed if required to monitor an on-going adverse event or other condition.

Participants are not supposed to change study sites; however, should this be necessary to allow a participant to continue in the study, participants will be analyzed under the site where they were initially enrolled.

Study day after first dose is defined as assessment date – first dose date +1. Dates prior to first dose are defined as assessment date – first dose date. Note that the protocol refers to “Day 0”; for the purposes of the datasets and analyses, this would appear as day 1.

All analyses will be performed using Statistical Analysis System (SAS®) Software version 9.3 or later.

Alpha levels are discussed in [Section 7.1.1.2](#) below; unless otherwise noted, 95% confidence intervals will be presented for statistical tests.

Presence of current tobacco/nicotine use and MDE is recorded first in the Interactive Web Response System (IWRS) during screening for purposes of randomization stratification and, after randomization, transcribed into the electronic data capture (EDC) system (as part of substance use history and the results for the MINI). The source for tobacco/nicotine use MDE in all analyses and statistical models will be the EDC data and not the IWRS.

#### **7.1.1 Adjustments for Multiplicity and Other Alpha Control**

##### **7.1.1.1 Multiplicity**

To adjust for multiplicity and to control for overall type I error, a fixed sequence procedure will be applied to key secondary efficacy endpoints. If the primary analysis produces a result that is statistically significant at a given level, the key secondary

endpoints will be tested in an ordered fashion at the same level. If the analysis for a secondary endpoint does not produce a statistically significant result, then the remaining secondary endpoint analyses will automatically be considered non-significant regardless of the p-value produced. In the case of an early stop or increase in sample size, the same methodology/critical value used for the primary endpoint will be applied to the key secondary endpoints for the purposes of the sequential testing.

The order in which the key secondary endpoints, intended for labeling purposes, will be tested is as follows:

- i. CGI-I score after 12 weeks of treatment (as a continuous outcome)
- ii. Change from baseline in the SDS total score after 12 weeks of treatment.

No other adjustments for multiplicity will be made and other p-values displayed in the output will be considered for descriptive summary purposes only and will not be used for formal inference. Additional details regarding statistical analysis for the listed endpoints can be found in [Section 9.2](#).

#### 7.1.1.2 Alpha Spend, Early Stops and Sample Size Increase

[REDACTED]

In the case of a sample size increase, the same inverse-normal method described in the primary efficacy analysis will be applied to the key secondary analyses to adjust the reported p-value; these will be tested at one-sided [REDACTED] to account for the first stage alpha spend.

#### **7.1.2 Data Handling for Participants Who Discontinue Study Drug or Withdraw from the Study**

Participants who withdraw/drop out from the study will have their ET visit data collected included in the analysis based on the closest visit window (Week 4, 8 or 12). Visit windows will be assigned by splitting the periods between visits at the midpoint between the visits. If more than one record falls within the window, the one closest to the target date will be used in the analysis.

#### **7.2 Efficacy Assessments**

There is one primary efficacy endpoint and two key secondary endpoints intended for the labeling. Other secondary and exploratory efficacy endpoints are tested to better understand the potential clinical benefit of TNX-102 SL on military-related PTSD participants.

### 7.2.1 Primary Efficacy

#### 7.2.2 Clinician-Administered PTSD Scale for DSM-5 (CAPS-5)

The primary efficacy endpoint is the change from baseline in total CAPS-5 score at Week 12 (Visit 6).

The CAPS-5 is an updated and validated version of a semi-structured interview that has been designed to assess the essential features of PTSD as defined by the DSM-5 (Weathers et al, 2013). The CAPS-5 affords the clinician flexibility to inquire about symptoms and diagnostic status over different time frames, such as past week, past month, and/or worst month for lifetime. For this study, a “Diagnostic” version of the CAPS-5 (past month recall) will be utilized at the Screening visit to confirm the diagnosis of PTSD and determine eligibility. A “Symptom Severity” version of the CAPS-5 (past week recall) will be completed by the clinician at all other time points (Baseline [Visit 2] and after 4, 8, and 12 weeks of treatment [Visits 4, 5, and 6]).

The CAPS-5 interview contains the following components

- Life Events Checklist for DSM-5 (LEC-5): Completed by the participant at the Screening Visit (Visit 1 only)
- Criterion A – Assessment Form (CA-AF): this semi-structured interview is based on the Criterion A discussion included in the CAPS-5, but modified (by [name], CAPS-5 lead author) specifically for this study to ensure sufficient review of the traumas outlined on the participant-completed LEC-5 and to capture clear description of the participant’s index/qualifying trauma (Visit 1 only)
- PTSD symptoms, onset/duration, distress/impairment, global rating, and dissociative symptoms:
  - o Criterion B: Items 1-5 (Intrusion symptoms)
  - o Criterion C: Items 6-7 (Avoidance symptoms)
  - o Criterion D: Items 8-14 (Negative alterations in cognitions & mood)
  - o Criterion E: Items 15-20 (Arousal and reactivity symptoms)
  - o Criterion F: Items 21-22 (Onset and duration of symptoms)
  - o Criterion G: Items 23-25 (Distress and impairment due to PTSD)
  - o Global ratings: Items 26-27 (Validity, severity)
  - o Dissociative symptoms: Items 29 (Depersonalization) and 30 (Derealization)

In addition to the total symptom score (obtained from the sum of Criteria B-E), the CAPS-5 affords the opportunity to examine clusters of symptoms, including Criterion B (intrusion symptoms), Criterion C (persistent avoidance), Criterion D (negative cognitions and mood), and Criterion E (arousal and reactivity), all of which will be secondary efficacy endpoints.

In the case of CAPS-5 items that are not resolvable at the site level (via query, review of source), the following conventions will be employed for handling of missing CAPS-5

items:

- For  $\leq 2$  missing item scores in Criterion B, D, or E, the average of the other items within the criterion will be used for the missing item;
- For  $< 2$  missing items scores in Criterion C, which only has 2 items, the value of the non-missing items will be used for the missing item;
- For  $> 2$  missing items in Criterion B, D, or E, or  $> 1$  missing item in the Criterion C, the total CAPS-5 score will be considered missing overall.

### 7.2.3 Key Secondary Efficacy Assessments

#### 7.2.3.1 Clinician Global Impression of Improvement (CGI-I)

The CGI-I will be completed by an Investigator to evaluate the participant's status since initiation of treatment. The CGI-I, status since initiation of treatment, is the first key secondary efficacy endpoint in this study. The CGI-I should be completed toward the end of each in-clinic post-Baseline study visit once all other assessments are available for the investigator's review. Once the participant has been randomized, an Investigator completes the CGI-I assessment after 4, 8, and 12 weeks of treatment in order to assess the overall change in the participant's status and answer the following question:

Since the initiation of treatment at Visit 2, the participant is:

- 1 = Very much improved
- 2 = Much improved
- 3 = Minimally improved
- 4 = No change
- 5 = Minimally worse
- 6 = Much worse
- 7 = Very much worse

The key secondary analysis of CGI will treat it as a continuous variable (scored 1-7 as above). There will be an additional outcome presented where a responder on the CGI-I is defined a participant who is scored as 'Very much improved' or 'Much improved' and compared between the study arms.

#### 7.2.3.2 Sheehan Disability Scale (SDS)

The SDS scale is a self-report questionnaire that was designed to assess the participant's view of the degree to which symptoms have disrupted work/school, social life/leisure activities, and family life/home responsibilities during the previous two weeks ([Sheehan & Sheehan, 2008](#)). In addition, the SDS asks the participant to provide the number of days of work/school lost as well as unproductive days in the past two weeks. The SDS scale will be completed by the participant at Baseline and after 4, 8, and 12 weeks of treatment (Visits 4, 5, and 6, respectively). A total score will be calculated summing the three individual 11-point (0-10) scales. For participants that do not respond to the work/school disruption because the participant checked the box indicating he/she has not worked or attended school for reasons unrelated to the disorder (PTSD), the total score will sum the other two domain questions and multiply by 1.5 (rounding up to the nearest whole number) to maintain the scale of 0-30 for the total score. Participants with missing

values on the other items will be missing for the total.

## 7.2.4 Other Efficacy Outcomes

### 7.2.4.1 PROMIS Sleep Disturbance Instrument

PROMIS refers to the Patient-Reported Outcome Measurement Information System ([www.nihpromis.org](http://www.nihpromis.org)), a National Institutes of Health (NIH)-funded initiative to develop instruments to be used across chronic conditions.

The PROMIS sleep disturbance scale (short form 8a) will be assessed at Baseline and after 4, 8, and 12 weeks of treatment (Visits 4, 5, and 6, respectively).

The sleep disturbance scale will be calculated summing the individual item scores of the 8 items. These summed scores will be transformed to T-scores using the published conversions (see [Section 14.2](#)).

### 7.2.4.2 Patient Global Impression of Change (PGIC)

The PGIC is a validated, self-report instrument to gauge the participant's assessment of change in condition. This form will be completed by the participant after 4, 8, and 12 weeks of treatment (Visits 4, 5, and 6, respectively). The participant will answer a single question:

Since the initiation of study medication, my PTSD symptoms are:

- 1 = Very much improved
- 2 = Much improved
- 3 = Minimally improved
- 4 = No change
- 5 = Minimally worse
- 6 = Much worse
- 7 = Very much worse

A responder on the PGIC is a participant who scores himself as 'Very much improved' or 'Much improved.'

### 7.2.4.3 BDI-II

The Beck Depression Inventory (BDI-II) is a 21-item measure of the severity of current depressive symptoms, extensively validated for use in both medical and mental health populations. While this instrument does not provide a psychiatric diagnosis of depression and has considerable overlap with PTSD associated symptoms, it does provide a continuous scale for measuring changes in the severity of symptomatology. The BDI-II will be completed by the participant at all visits.

### 7.2.4.4 CAPS-5 Additional Endpoint Definitions

#### 7.2.4.4.1 Response

Response is defined as  $\geq 10$ -point improvement from baseline in CAPS-5 total score.

#### 7.2.4.4.2 Loss of Diagnosis

Loss of Diagnosis at any time point is defined as Response AND no longer meeting DSM-5 symptom criteria required for diagnosis on the CAPS-5 in any one or more of the four clusters (B, C, D, E).

#### 7.2.4.4.3 Sustained Remission

Remission at any time point is defined as a Loss of Diagnosis and a CAPS-5 total score of  $\leq 10$ . Remission that is sustained is defined by meeting remission criteria after both 8 AND 12 weeks of treatment.

A CAPS-5 total score of  $\leq 10$  was selected for remission based on [name] (National Center for PTSD) communication that empirical data suggested the CAPS-5 score range from 0 to 10 was “asymptomatic/few symptoms”. In large multicenter pharmacotherapy trials of PTSD that utilized the prior 17-item CAPS for DSM-IV, remission was defined as achieving a score of  $< 20$  (Krystal et al, 2011) or  $\leq 20$  (Davidson et al, 2006). Direct mathematical extrapolation of a score of 20 on prior CAPS version, considering the different scaling for intensity/frequency (0-4 on CAPS-5; 0-8 on CAPS for DSM-IV), would be  $((\text{remission score of } 20 / 17\text{-items CAPS for DSM-IV}) / 2 \text{ (scaling)}) * 20\text{-items CAPS-5} = 11.8$  or about 12. Although  $< 12$  or  $\leq 12$  were considered as more comparable with these definitions from studies using the prior version of CAPS, the definition of  $\leq 10$  was ultimately chosen as the more stringent approach.

### 7.3 Safety Assessments

Safety will be assessed by:

- AE and SAEs throughout the entire duration of the study, including detailed assessment of AEs involving the oral cavity.
- Changes from baseline in clinical laboratory test results.
- Changes from baseline in vital signs and weight.
- Change from baseline in BDI-II (see Section 7.2.4).
- Changes from baseline indicative of increased suicidal ideation or behavior as assessed by the C-SSRS.
- Changes from baseline in participant-rated CSFQ-14.
- Changes from baseline in participant-rated morning sedation as assessed by the MTRSS.

#### 7.3.1 Adverse Event and Prior/Concomitant Medication handling conventions

To handle missing or partial AE and prior/concomitant medication dates, the following rules will be applied.

For partial start dates:

1. If the year is unknown, then do not impute the date but assign a missing value.
2. If the month is unknown, then:

- a. If the year matches the year of the first dose date, then impute the month and day of the first dose date.
  - b. Otherwise, assign “January.”
3. If the day is unknown, then:
- a. If the month and year match the month and year of the first dose date, then impute the day of the first dose date.
  - b. Otherwise, assign “01.”

For partial end dates:

1. If the year is unknown, then do not impute the date but assign a missing value.
2. If the month is unknown, then assign “December.”
3. If the day is unknown, then assign the last day of the month.

Adverse events are categorized as either pre-treatment adverse events or treatment-emergent adverse events based on the response to the CRF question “Did the AE start prior to the first dose?”

After implementing the rules above, to determine whether medications with missing start or stop dates are prior or concomitant medications, the following strategy will be used:

1. If the start date and stop date are both missing, then the most conservative approach is taken and the medication is considered to be a concomitant medication.
2. If the start date is missing but the stop date is not missing and is after the day of first study dose administration, then the most conservative approach is taken and the medication is considered to be concomitant.
3. If the start date is missing but the stop date is not missing and is on or before the day of first study dose and after the date of signed informed consent, then the medication is considered to be a prior medication.
4. If the start date is not missing but the stop date is missing, then the most conservative approach is taken and medication is considered to be concomitant.

The missing severity of an AE will be imputed to “severe”; the missing relationship to study drug of an AE will be imputed to “related”.

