11.3.1. Adverse Events (AEs)

Patients will be monitored for AEs throughout the study from the time that the patient signs an informed consent and onward. AEs that are spontaneously reported, elicited or observed are to be recorded on the CRF with the date, time of onset, date and time of resolution, severity, seriousness, causality (relationship to study medication), actions required, and outcome.

To elicit AEs, non-leading, simple questions with minimal connotations should be used as the initial questions at all evaluation points during the study. Examples of these questions can be:

- How have you felt since your last visit?
- Have you had any health problems since your last visit?

If an AE occurs, the investigator will institute support and/or treatment as deemed appropriate. If a non-serious AE is unresolved on the last day of the study, an effort should be made to follow up until the AE is resolved or stabilized, the patient is lost to follow-up, or there is some other resolution of the event.

There are many symptoms associated with PTSD that can vary in intensity and frequency over time. Only symptoms that significantly worsen or become more frequent, in the opinion of the patient and outside of their normal experience, should be reported as an adverse event.

If a patient reports an oral cavity adverse event, the Investigator should examine the oral cavity to confirm the presence or absence of any irritation or other signs. Additional details related to onset, duration, severity and reversibility of the oral cavity event will be documented ([Section 11.3.5](#)).

Additional information regarding definition and reporting requirements for adverse events, serious adverse events, and pregnancies is provided in [Section 11.3.1](#).

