12. DEFINITIONS, RECORDING, AND REPORTING OF ADVERSE EVENTS

12.1. Definition of Adverse Events

According to International Conference on Harmonization (ICH) guidance E2A, Clinical Safety Data Management: Definitions and Standards for Expedited Reporting, an adverse event (AE) is

any untoward medical occurrence in a patient or clinical investigation patient administered a pharmaceutical product and which is not necessarily required to have a causal relationship with this treatment. An AE can therefore be any unfavorable and unintended sign (including an abnormal laboratory finding, for example), symptom, or disease temporally associated with the use of a medicinal product, whether or not considered related to the medicinal product.

A treatment-emergent AE (TEAE) is an AE that either commenced following initiation of study treatment or was present prior to study treatment but increased in frequency or severity following initiation of study treatment.

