### **10.1 Adverse Events**

All AEs, treatment-emergent adverse events (TEAEs), and SAEs will be coded using MedDRA, version 19.0.

TEAEs are defined as either new onset AEs with an onset at the time of or following the start of treatment through ten days after the last dose of study medication, or a recurrence of an AE (or medical history) present prior to randomization but increasing in severity, frequency or relationship at the time of or following the start of treatment

An AE summary table will be presented for the following:

- TEAEs by severity
- TEAEs leading to study drug discontinuation
- TEAEs by relationship
- SAEs

Summaries of incidence rates (frequencies and percentages) of individual AEs by MedDRA SOC and preferred term will be prepared. Such summaries will be displayed for all TEAEs, TEAEs by maximum severity, and TEAEs by strongest relationship to study drug.

Each participant will be counted only once within each summation level (SOC; preferred term). If a participant experiences more than one TEAE within each summation level only, the TEAE with the strongest relationship or the maximum severity, as appropriate, will be included in the summaries of relationship and severity.

Adverse events of special interest pertaining to abuse potential (as defined in the January 2017 Assessment of Abuse Potential for Drugs – Guidance for Industry) will be analyzed separately by treatment group, SOC and preferred term, and displayed in tabular format.

In the AE data listings, all AEs will be displayed. AEs that are treatment-emergent will be flagged.

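### SAP 7.3.1 and SAP 10.1 give conflicting rules for treatment-emergent status with no stated precedence, so an event that starts before dosing and worsens on drug can be left out of the TEAE tables

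*SAP*

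**What the plan says.** SAP 7.3.1 opens as a section on incomplete dates: "To handle missing or partial AE and prior/concomitant medication dates, the following rules will be applied". After the partial-date rules it adds a sentence with no such limit: adverse events are "categorized as either pre-treatment adverse events or treatment-emergent adverse events based on the response to the CRF question", the question being "Did the AE start prior to the first dose". The answer gives a two-way split.

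SAP 10.1 defines a TEAE differently. One limb is a new event with onset from the start of treatment "through ten days after the last dose of study medication". The other is "or a recurrence of an AE (or medical history) present prior to randomization but increasing in severity, frequency or relationship" once treatment has begun.

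Protocol 12.1 counts an event that starts after treatment begins, with no end date, and one that "was present prior to study treatment but increased in frequency or severity following initiation of study treatment".

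On collection, Protocol 11.3.1 states: "Patients will be monitored for AEs throughout the study from the time that the patient signs an informed consent and onward". The screening period that precedes dosing is 7 to 35 days (Protocol 10.1.2).

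**The concern.** A question about onset cannot carry out the worsening limb that both SAP 10.1 and Protocol 12.1 contain, and it cannot apply the ten-day limit in SAP 10.1. Section 7.3.1 is nevertheless the only place in the SAP that tells a programmer how to set the category. Two programmers working from the same SAP could produce different TEAE counts.

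The summaries by system organ class and preferred term (all TEAEs, by maximum severity, by strongest relationship) and the table of TEAEs leading to discontinuation all depend on this status. Events that begin before dosing are plausible here. Collection starts at consent, adverse events are assessed at Visit 2 before randomization, and some patients taper excluded medication during screening. An event that begins in that interval and worsens on drug is one that a safety table is meant to show.

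**Working it through.** No arithmetic applies. The check sets the three rules side by side.

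Inputs:
- SAP 7.3.1: status follows the CRF answer on onset.
- SAP 10.1: new onset up to last dose plus ten days, or a pre-existing event or history that increases.
- Protocol 12.1: new onset after treatment starts, or a pre-existing event that increases; no end limit.

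| Case | SAP 7.3.1 | SAP 10.1 | Protocol 12.1 |
|---|---|---|---|
| 1. New onset on drug | TEAE | TEAE | TEAE |
| 2. Onset before first dose, no worsening | not | not | not |
| 3. Onset before first dose, worsens in severity or frequency on drug, kept on one record | **not** | TEAE | TEAE |
| 4. Pre-existing event or history worsens on drug, entered as a new record with a post-dose start | TEAE | TEAE | TEAE |
| 5. New onset more than ten days after last dose | TEAE | **not** | TEAE |
| 6. CRF answer missing | no rule | by definition | by definition |

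Reading the table:
- SAP 7.3.1 conflicts with SAP 10.1 in cases 3 and 5, and with Protocol 12.1 in case 3 only.
- Cases 3 and 4 can be the same clinical event. They differ only in how the site records it, and neither document states a recording rule.
- Case 3 errs by omission from the TEAE tables. Case 5 depends on which definition is meant, because the protocol has no ten-day limit.

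What a case 3 event would still appear in:
- The SAE table (SAP 10.1.2), if serious, since that table is not restricted to TEAEs.
- The AE listings (SAP 10.1), which show every event, although this one would lack the treatment-emergent flag.
- The listing of events leading to discontinuation (SAP 10.1.1), if it led to discontinuation; that listing is worded as AEs.

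How often case 5 can arise: the schedule in Protocol Appendix 1 has no routine safety visit after Week 12, and SAP 7.1 follows early terminators only for an ongoing event or condition. However, Protocol 10.5.1 encourages an early termination visit even after a lapse in medication. Such events are possible but should be few.

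Whether the fix can be derived: the AE fields listed in Protocol 11.3.1 include onset, resolution, severity, seriousness, causality, actions and outcome. No date of worsening is listed. Where worsening stayed on the original record, the listed fields may not show when it occurred.

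**The case against.** The strongest answer is that case 3 may never arise. If sites enter worsening as a new event, the CRF answer is no and the event is counted. For PTSD symptoms, Protocol 11.3.1 makes the worsening itself the reportable event, so its natural onset date falls after the first dose. Pre-existing medical history would likewise reach the AE data through a new entry. What remains is narrow: an event that first appears between consent and first dose, persists, worsens on drug and is kept on one record. This stands, and it limits the size of the problem. It does not remove it, because the recording rule for such events is nowhere stated.

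A second answer is that SAP 10.1 holds the formal definition in the AE analysis section, while 7.3.1 concerns dates. This stands in part. A reader might infer from 7.3.1 that the SAP's TEAE definition is not applied at all. The documents do not show that; they show two unreconciled rules. But the sentence in 7.3.1 is unconditional, so it cannot be read as a fallback for missing dates either.

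A reader might also infer that every worsened pre-existing event drops out of every TEAE table, or that the rule hides a drug signal. Neither follows. The loss depends on recording practice, and the SAE table and listings do not depend on the flag. Change in mood, suicidality, morning sedation and sexual function is also measured by BDI-II, C-SSRS, MTRSS and CSFQ-14.

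Finally, on the ten-day limit, 7.3.1 agrees with the protocol, and any error there over-counts. That is correct, and it means the limit needs reconciling with Protocol 12.1 as well as within the SAP.

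**Conclusion.** The contradiction is real and should be corrected. Read as written, SAP 7.3.1 classes as pre-treatment some events that SAP 10.1 and Protocol 12.1 both count as treatment-emergent. It also classes as treatment-emergent some late events that SAP 10.1 excludes and the protocol includes. The tables at risk are the TEAE summaries (overall, by severity, by relationship) and the TEAE discontinuation table. No efficacy result is affected.

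The size cannot be computed. The documents give no rate of events starting before dosing and no rate of worsening, so any percentage would rest on unsourced inputs. The lower bound is zero, reached if worsening is always entered as a new record. A loss requires that at least some worsening is kept on the pre-dose record and that the programmer follows 7.3.1 rather than 10.1.

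**What to change.** 1. State in SAP 7.3.1 that the definition in SAP 10.1 governs treatment-emergent status.
2. Derive the flag from the AE start date (after the partial-date rules), the first and last dose dates, and any recorded worsening on or after the first dose.
3. Use the CRF answer only where dates cannot settle onset. Examples are a start date that is missing, one imputed to the first-dose date, or an onset on the day of first dose, since dosing is at bedtime. Say what happens when the answer is missing.
4. State that worsening of an event that began before dosing is entered as a new record, with the date of worsening as its onset.
5. Reconcile the ten-day limit in SAP 10.1 with Protocol 12.1, which has none, and list any remaining difference in SAP section 12 as a change from the planned analysis.

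The cost is a few sentences in the SAP, one revised derivation, and a recording instruction to sites. Where worsening has already been kept on the original record, a data check or query is also needed, because the AE fields listed in the protocol include no date of worsening.
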